## ***ii. Study Design***

### **a) Experimental Group:**

Upon enrollment in the study, patients in the experimental group will be requested to do the following for their participation in the study:

- Follow standard of care, which includes access to MyChart

#### **Separate from standard of care:**

- Receive an AdhereTech smart pill bottle to use for dispensing their anticoagulation medication at home.
- Receive training on the use of the AdhereTech smart pill bottle and commit to using in their daily routine for their anticoagulant medication
- Receive one-on-one training aimed at use of the MyChart PHR
- Use the PHR intervention: patients in this group will have the MyChart intervention designed and built in Phase 1 of this study – tailored health messaging delivered via MyChart pertinent to non-valvular atrial fibrillation and oral anticoagulation and stroke.
  - In addition to the tailored health messaging, patients will also receive periodic messages asking them to evaluate the health information they have received.
- Participate in an initial study visit, which includes the enrollment and training process above, as well as one follow up study visit and exit interview at approximately 6 months.
- Complete a patient survey at the initial study visit and follow up visit at approximately 6 months
- Submit information about their prescription history related to their anticoagulant medication for the study period
  - Patients may obtain this information from their pharmacy or print it out from their online pharmacy account. Patients will receive a letter from the Principal Investigators and a Medication dispensing record form to provide to their Pharmacist requesting anticoagulant dispensing information required for the study. The printout will be collected by the patient or a study representative with permission from the patient.

### **b) Control Group:**

Upon enrollment in the study, patients in the control group will be requested to do the following for their participation in the study:

- Receive a smart pill bottle to use for dispensing their anticoagulation medication at home.
- Receive training on the use of the smart pill bottle and commit to using in their daily routine for their anticoagulant medication
- Follow standard of care, which includes access to MyChart
- Receive one-on-one training aimed at use of the MyChart PHR
- Participate in an initial study visit, which includes the enrollment and training process above, as well as one follow up study visit and exit interview at approximately 6 months.
- Complete a patient survey at the initial study visit and follow up visit at approximately 6 months
- Submit information about their prescription history related to their anticoagulant medication for the study period
  - Patients may obtain this information from their pharmacy or print it out from their online pharmacy account. Patients will receive a letter from the Principal Investigators and a Medication dispensing record form to provide to their Pharmacist requesting anticoagulant dispensing information required for the study. The printout will be collected by the patient or a study representative with permission from the patient.
- At the conclusion of the study, participants in the control group will be sent a link to access the tailored health messaging sent to the experimental group, delivered via MyChart.

c) Quantitative Data Collection and Analysis:

Besides age, gender, and basic demographics, we will perform detailed testing using six instruments to quantify patient characteristics; 1) the System Usability Survey (SUS), a commonly used ten question evaluation tool with Likert-scale responses to identify comfort with technology, 2) the Medication Adherence Survey (MAS), an eight question survey that is well validated to predict medication compliance, 3) the Patient Activation Measure (PAM), a 13 question survey well-validated to measure patient engagement, 4) the Atrial Fibrillation Knowledge Scale, an 11 item survey designed to assess AF understanding, 5) Newest Vital Sign a six-question health literacy survey, 6) Altarum Consumer Engagement

(ACE) Measure, a 12 question survey validated to measure patient engagement, and 7) Ten-Item Personality Inventory (TIPI), a ten question survey used to assess patient personality. The first six survey instruments will be incorporated into a baseline and follow-up patient survey to be built out in Survey Monkey®, an on-line tool to design, collect and analyze surveys and responses. The TIPI survey will be used only at the 6-month study follow-up visit. Survey Monkey enables covered entities to collect protected health information (PHI) in online surveys in a way that permits compliance with the Health Insurance Portability and Accountability Act of 1996 (HIPAA). SSL (Secure Sockets Layer), a protocol developed for transmitted private documents or information via the internet, creates a secure connection between a client and a server, encrypting sensitive information being transmitted through the web page. After consenting participants, we will ask them to complete demographic information and survey (Table 2).

Patient surveys will be comprised of questions aimed at assessing patient engagement, health literacy, and medication adherence. Patient engagement will be assessed using the validated survey instruments, the Patient Activation Measure (PAM) and the Altarum Consumer Engagement (ACE) Measure, number of logins to MyChart and secure messaging activity with provider/health coach. We will also evaluate health literacy using questions aimed at patient understanding of anticoagulant use in AF. Medication adherence will be measured using the MAS validated survey instrument developed by Morisky and patient pharmacy refill records. In an attempt to make the medication adherence data more robust, we will extract refill record data from electronic prescribing software (Surescripts) on study patients. In addition, all patients will use smart pill bottles to dispense their anticoagulation medication. These bottles will track medication adherence by the opening of the bottle cap, and will record data accordingly. The bottles will not be set up to alert patients or deliver any intervention for medication adherence.

In order to determine the exact tailored health messaging patients will receive, study staff will identify the following information in patients' electronic health records:

1. Duration of time since AF diagnosis (Approximate days, months, and/or years)
2. Current oral anticoagulant prescribed

3. Duration of time since beginning to take the above anticoagulant (Answer in approximate days, months, and/or years)
4. History of switched anticoagulant
5. If yes to above, type of anticoagulant taken before current one

Concurrent with the educational messages sent to patients through MyChart, patients will periodically be sent a short survey asking them to evaluate the health information they just received.

In addition, to measure the impact of the intervention we will collect specific health outcomes related data, PHR login frequency, and frequency of calls to the clinic. Quantitative measures of both study groups, control and experimental will be collected on both study groups, 6 months prior to beginning of study to baseline and baseline to end of 6-month trial.

- 1) Major Adverse Events: Death, Stroke, Any Embolic Event, Major Bleeding (transfusion)
- 2) Health Care Utilization: Hospitalization, ER visits, Office Visits, Calls to Office

See Table 3 for all quantitative measures, purpose and timing of collection.

All data will be aggregated by Parkview Research Center (PRC) and statistical analysis will be performed by PRC and the Indiana University School of Medicine, Department of Biostatistics. Additional consultants, partners, or business associates will be utilized as necessary.

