Purpose	
This study is designed to develop patient focused strategies that improve adherence to anticoagulant medication in patients with non-valvular atrial fibrillation (AF). There are two phases to the study: Intervention Development and Intervention Trial. The intervention to be developed during Phase 1 includes tailored health education messaging delivered through a personal health record, MyChart. During the development of the intervention in Phase 1 we will use a patient-centered, iterative design process that includes interviews, prototype development and testing. One trigger for health education messaging will be failure to take, fill, or refill anticoagulant medication prescription – information obtained from an e-prescribing data feed to the electronic medical record (Surescripts) and use of a smart pill bottle (AdhereTech – HIPAA compliant, FDA-registered Class I medical device) that sends notification in real time when participants open or fail to open their pill bottle. The intervention trial in Phase 2 will be comprised of two groups, control and experimental. Both the control and experimental group will receive standard care, which includes access to MyChart. In addition to standard care, both groups will receive training on the use of MyChart and the AdhereTech smart pill bottle, and medication adherence for both groups will be monitored with Surescripts e-prescribing software and AdhereTech smart pill bottle use. The experimental group will receive the intervention: tailored health messaging delivered via MyChart pertinent to AF and oral anticoagulant use. Outcomes of this work include a novel intervention, as well as information regarding patient preferences for tailored education.
 
Specific Aims: Aim 1: Determine AF patient preference for content, timing, and delivery mode of tailored educational information about AF and anticoagulant therapy; Aim 2: Determine the impact of tailored messaging via personal health record on adherence to anti-thrombotic therapy and health outcomes in people living with AF; Aim 3: Determine the feasibility of measuring medication adherence with queries to electronic prescribing software and use of ‘smart’ pill bottles.

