## 2.) PHASE 2: INTERVENTION TRIAL

*Aim 2: Determine the impact of tailored messaging via personal health record on adherence to anti-thrombotic therapy and health outcomes in people living with AF.*

*Aim 3: Determine the feasibility of measuring medication adherence with queries to electronic prescribing software and use of ‘smart’ pill bottles.*

During the last 12 months of our study, we will conduct a 6-month trial of the intervention designed and built in Phase 1 of the study to examine the impact on patient engagement and medication adherence. Patients who meet inclusion criteria and agree to participate will be randomly assigned to one of two groups – Experimental or Control. The research team will alternate random assignment to experimental or control group in order to achieve equal numbers of patients receiving VKA and NOAC medication across both groups. Please see Figure 2 below, outlining the study group assignment process.

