**Figure 2: Tech Trial Study Group Assignment Process**

### ***i. Patient Selection***

- a) Study Population: The study population is comprised of all adult, ambulatory PPG-Cardiology patients with non-valvular atrial fibrillation who are taking an oral anti-coagulant medication
  
- a. Sample Size: Approximately 160 patients (80 Control/80 Experimental Groups; randomized/un-blinded)

\*Based on prior data, the within-group standard deviation of the medication possession ratio (MPR) is estimated to be 10%. MPR is considered a continuous variable and sample size calculations are based on comparing the difference in two mean MPR values. With a final sample size of 64 subjects per group completing the study, the study will have 80% power to detect a 5% difference in MPR between groups, assuming two-sided tests each conducted at a 5% significance level. To account for a 20% dropout rate, 80 subjects will be enrolled per group.

b) Inclusion/Exclusion Criteria:

Inclusion Criteria

1. Diagnosis of Atrial Fibrillation (Paroxysmal, Persistent, Permanent)
2. Receiving Oral Anticoagulation (VKA or NOAC) for non-valvular AF
3. Physically and Mentally capable of providing Informed Consent
4. Age 18 years or older
5. Access to Computer and Internet
6. Ability to read and understand English
7. Current Patient of PPG-Cardiology
8. Willing to have a MyChart account

Exclusion Criteria

1. Absence of History of Atrial Fibrillation (AF)
2. Does not meet Inclusion Criteria
3. Anticoagulation with VKA or NOAC for reasons other than non-valvular AF
4. Prescribed the anticoagulation medication Dabigatran, as this specific NOAC cannot be transferred from its original pill bottle to the study smart pill bottle
5. Unable to physically or cognitively carry out the tasks necessary for utilizing a PHR such as; blindness, loss of function of arms, cognitive impairments (per chart review) that would interfere in learning a new task
6. Designated as part of a vulnerable subject population that the investigator or designee identifies to have compromised autonomy related to potential study participation
7. Currently participating in another Parkview study that involves PHR use
8. Not willing to have a MyChart account

9. Previously participated in the study focus groups
10. Previously participated in the study design sessions

c) Enrollment:

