Alcohol Use	Y/N	EHR	Risk for Bleeding: HAS-BLED		√	
Arterial embolus	Y/N	EHR	Health outcome	6 mo. – Baseline		Baseline – 6 mo.

Hemorrhage	Y/N	EHR	Health outcome	6 mo. – Baseline		Baseline – 6 mo.
Hospitalizations	Y/N	EHR	Health outcome	6 mo. – Baseline		Baseline – 6 mo.
Stroke	Y/N	EHR	Health outcome	6 mo. – Baseline		Baseline – 6 mo.
Death	Y/N	EHR	Health outcome	n/a		Baseline – 6 mo.
Calls to Anticoagulation Treatment Unit (ATU)	Numeric	ATU	Burden/ Patient Engagement	6 mo. – Baseline		Baseline – 6 mo.
Prescription Refill Frequency	Numeric	EHR	Assess medication adherence	6 mo. – Baseline		Baseline – 6 mo.
Smart Pill Bottle Use	Numeric	Report	Daily report of pill bottle opening, date/time stamped		√	√
MAS	Numeric	Survey	Assess medication adherence		√	√
PAM	Numeric	Survey	Assess patient engagement		√	√
SUS	Numeric	Survey	Computer use self-efficacy		√	√
AF Knowledge Scale	Numeric	Survey	Assesses knowledge of AF disease		√	√
New Vital Sign	Numeric	Survey	Assesses health literacy		√	√
ACE	Numeric	Survey	Assess patient engagement		√	√
TUPI	Numeric	Survey	Assess patient personality			√
PHR Login Frequency	Numeric	EHR	Assess engagement	6 mo. – Baseline		Baseline – 6 mo.
PHR webpage and video view frequency	Numeric	EHR	Assess engagement			Baseline – 6 mo.
PHR messages/phone calls to study staff	Numeric/Qualitative	EHR	Burden/ Patient Engagement			Baseline – 6 mo.
Appointments scheduled	Numeric	EHR	Assess engagement			Baseline – 6 mo.

\*See Appendix for scoring of HAS-BLED risk for bleeding and CHA2DS2\_VASc risk of stroke

d) Qualitative Data Collection and Analysis:

We will conduct semi-structured interviews at the conclusion of the 6-month study period with all participants in both the control and experimental groups. This data will act to fill the gaps that remain in survey data, as it allows for a deeper examination of particular issues with people living with AF. Participants will be asked questions in order to flesh out more detail around the usage patterns of the tested technologies, patient engagement, technology acceptance and experience with patient-provider communication.

All interviews will be audio recorded, with participant permission and researchers will take field notes. Investigators will review the transcribed digital recordings and field notes and perform thematic analysis to develop

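### In this un-blinded trial the protocol lets the arm be known during the shared training and baseline survey, because it does not place those steps before assignment

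*Protocol*

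**What the plan says.** The Protocol Synopsis sets a common background package: "both groups will receive training on the use of MyChart and the AdhereTech smart pill bottle". The tailored messages sent through MyChart are the planned difference between the arms.

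Under 2.) Phase 2: Intervention Trial, assignment follows agreement to take part: "Patients who meet inclusion criteria and agree to participate will be randomly assigned to one of two groups". The method is given as "The research team will alternate random assignment to experimental or control group", with the aim of balancing VKA and NOAC users. Section i. Patient Selection gives the size and the lack of blinding: "Approximately 160 patients (80 Control/80 Experimental Groups; randomized/un-blinded".

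Section ii. Study Design then lists procedures arm by arm. Part a) opens "Upon enrollment in the study, patients in the experimental group will be requested to do the following for their participation in the study"; part b) opens "Upon enrollment in the study, patients in the control group will be requested to do the following for their participation in the study". Each list contains bottle training, a survey at the initial visit, and the item "Receive one-on-one training aimed at use of the MyChart PHR". Each also says that the initial visit covers enrolment and training together.

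Part c) Quantitative Data Collection and Analysis says that the survey is completed once consent has been given. It does not say whether that is before or after assignment. Figure 2, to which the protocol refers for the assignment process, was not available in the text reviewed.

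**The concern.** The comparison isolates the messages only if everything else given to the two arms is the same. One-on-one training is the component most open to variation, because a person delivers it. A trainer who knows that a patient will receive MyChart messages has a reason to spend longer on finding and opening them, or to talk more about adherence.

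The protocol's own pilot, described under Study Background, shows why equal training matters. There the intervention was one-on-one MyChart training plus newsletters, against controls with neither, and knowledge and MPR rose significantly only in the intervention group. The pilot cannot say how much of that came from training, and the present trial could not say so either if training differed by arm.

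The second route is the baseline survey. A participant who already knows the arm may answer questions on adherence, activation, engagement or computer confidence differently. Any analysis that uses those baseline scores would then use a value already touched by allocation.

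The outcomes closest to the training content are MyChart logins and page views, SUS, PAM, ACE and the self-reported MAS.

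**Working it through.** **1. What the text fixes about order**

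| Step | Where described | Order relative to assignment |
|---|---|---|
| Consent | i. Patient Selection, c) Enrollment | Before enrolment |
| Assignment | Opening of 2.) Phase 2 | After agreement to take part; nothing further |
| MyChart and bottle training | ii. Study Design, a) and b) | Initial visit, listed for patients already named by arm |
| Baseline survey | ii. Study Design, a), b) and c) | Initial visit, after consent; not tied to assignment |

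Two sequences fit: consent, assignment, training and survey; or consent, survey and training, assignment. The arm-wise lists favour the first for training. For the survey, part c) leaves both equally open. No text available says that assignment comes last, that trainers are unaware of the arm, or that training follows a fixed script.

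**2. Whether the visit needs the arm to be known**

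The training and survey items appear in both lists. The items found only in the experimental list are the messages and the requests to evaluate them, both sent remotely. The item found only in the control list is a link sent at the end of the study. Nothing done at the initial visit depends on the arm.

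**3. Whether the sample size is affected**

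Inputs from i. Patient Selection: difference 5 points, SD 10, two-sided 5% level, 80% power, 20% dropout.

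- Normal approximation: n = 2 × (1.960 + 0.842)² × 10² / 5² = 62.8, so 63 per group.
- Two-sample t-test: 63.77, so 64 per group; power at 64 is 0.801.
- Dropout: 64 / (1 − 0.20) = 80 per group.

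The stated 64 and 80 are reproduced. Reordering the visit changes none of the inputs.

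**4. How sensitive the MPR comparison would be (illustration only)**

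The document gives no size for a training difference, so the shift b below is assumed. With 64 completers per group and SD 10, SE = 10 × √(2/64) = 1.768. If messaging had no effect and unequal training alone moved mean MPR by b, the chance of a significant result is 1 − Φ(1.96 − b/SE) + Φ(−1.96 − b/SE):

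| Assumed b (MPR points) | b/SE | Chance of rejection |
|---|---|---|
| 0.5 | 0.28 | 5.9% |
| 1 | 0.57 | 8.7% |
| 2 | 1.13 | 20.5% |
| 3 | 1.70 | 39.6% |

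**5. The survey route**

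Suppose that knowing the arm shifts a baseline score by d in one arm and leaves the follow-up score unchanged. A comparison of raw change is then biased by the whole of d in the opposite direction. A baseline-adjusted comparison is biased by d times the regression slope, and a comparison of follow-up scores alone is not biased by it. The protocol does not fix which is used, and it gives no basis for a value of d. Dispensing-based MPR uses no self-report, so this route does not reach it.

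**The case against.** The strongest reply is that lists of duties by arm are an ordinary layout and not a timetable. The same lists include the six-month visit, the exit interview and pharmacy records, and the experimental list names the messaging before it names the initial visit. The survey is tied only to consent, and Figure 2 may settle the order. This stands against any claim that the arm **is** fixed before training and the survey. A reader might infer that from the lists, but no sentence says so. The narrower point is untouched: the text permits that order and contains no safeguard against it.

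It is also fair that both arms are specified to receive the same training and that the lack of blinding is declared openly. There is no evidence that the packages differ. The bottle is named by brand in one list and not in the other, but the Synopsis gives the same bottle to both groups.

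Two further readings are tempting and should not be made.

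- Table 3 ticks smart-bottle use at baseline, described as "Daily report of pill bottle opening, date/time stamped", although the bottle is handed out at that visit. A reader might conclude that no bottle reading before the first message can exist. The protocol gives no date for the first message, staff must first look up record items to select messages, and the tick may mean only that recording starts then.
- A reader might set an assumed bias in survey scores against the 0.5 SD (5/10) that the trial is sized for. That target is for MPR, a different variable, so the comparison has no meaning.

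Finally, reordering alone would not be enough. If assignment literally alternates, staff can foresee the next arm whenever it is announced. This stands, and the fix has to cover it.

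**Conclusion.** The point holds as a gap in the stated order of steps. In an un-blinded trial, the protocol as written allows trainer and participant to know the arm during the one-on-one training and the baseline survey. A training difference by arm would be credited to the messages, and the self-reports MAS, PAM, ACE and SUS are open to arm-aware answers at baseline.

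The size is unknown. The MPR table shows only what assumed shifts of 0.5 to 3 points would do to the false-positive rate; it is no evidence that a shift occurs. MPR is the less exposed outcome, since training could reach it only by changing behaviour.

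The conclusion rests on the text available. If Figure 2 already puts assignment after survey and training, what remains is to bring the arm-wise lists into line with it and to remove the alternation. The change deserves to be made because it costs almost nothing, not because bias has been shown.

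**What to change.** In the opening of 2.) Phase 2 and in ii. Study Design, parts a) and b):

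1. Describe consent, baseline survey, MyChart training and bottle training once, for all participants, and say that the training content is the same for everyone.
2. State that the assignment is revealed only after these steps are complete. The arm-specific lists then begin with what differs.
3. Replace the alternating assignment with a randomly generated sequence, stratified by VKA or NOAC to keep the intended balance, and concealed from the staff who recruit and train so that the next arm cannot be foreseen.
4. Check that Figure 2 shows the same order.

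The cost is a few sentences and the preparation of a concealed list. Because the messages are sent remotely, the arm can be revealed at the end of the same visit. No extra visit or staff, no waiting period before messaging and no change to the 80 per group are needed. The change does not blind anyone after assignment, so later contact with study staff and the follow-up self-reports remain open-label.

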During enrollment, patients will be instructed to contact study staff if their anticoagulant medication is changed or permanently discontinued at any point during the study. If their anticoagulant medication is permanently discontinued, patients will be instructed to stay in the study even while they are not taking their anticoagulant. Sometimes patients' anticoagulation therapy is temporarily discontinued for surgery or other health reasons. In order to maximize patient safety when these temporary holds on medications occur, tailored messages related to medication administration and compliance will include a disclaimer that if their medication has been stopped then this information is supplementary and they should follow their doctor's instructions first and foremost.

Concurrent with the educational messages sent to patients through MyChart, patients will periodically be sent a short survey asking them to evaluate the health information they just received. These questions will enable patients to evaluate the content, timing and delivery format of the interventional messaging. The survey will be administered through Survey Monkey, and the MyChart message will contain a secure link to access the survey.

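### Table 3 records hospitalizations and clinical events as one yes/no per six-month window without count or date, and has no usable before/after rows for ER and office visits

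*Protocol*

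**What the plan says.** Protocol, Phase 2, Study Design, part c) Quantitative Data Collection and Analysis, names two groups of measures meant to show the impact of the intervention: major adverse events, and "Health Care Utilization: Hospitalization, ER visits, Office Visits, Calls to Office". Both are to be collected in both arms over the six months before baseline and the six months of the trial. The section refers to Table 3 for the complete set of quantitative measures.

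Table 3 fixes these types:

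- Admissions: "Hospitalizations Y/N EHR Health outcome", one entry for each window.
- Clinical events, one entry for each window: "Stroke Y/N EHR Health outcome", "Hemorrhage Y/N EHR Health outcome" and "Arterial embolus Y/N EHR Health outcome".
- Death: "Death Y/N EHR Health outcome", trial window only.
- Calls, by contrast, are counted in both windows: "Calls to Anticoagulation Treatment Unit (ATU) Numeric ATU". Prescription refills and portal logins are also numeric.
- Scheduled appointments, the nearest row to office visits, are numeric but collected only after baseline, with engagement as the stated purpose.
- ER visits have no row.

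Elsewhere, the Subject Withdrawal section limits the usable data of a withdrawn patient to the period before withdrawal, and the sample-size note plans for 20% dropout. Part e) Intervention says that after permanent discontinuation "patients will be instructed to stay in the study even while they are not taking their anticoagulant".

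**The concern.** The text treats hospitalization as utilization, but the table stores only whether there was at least one admission. A patient with three admissions before baseline and one during the trial is coded yes, then yes.

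The missing date has a separate cost. With one yes/no for the whole trial window, the stored data cannot show whether an event in a withdrawn patient fell before or after withdrawal. A yes from two months of observation also looks the same as a yes from six.

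For two of the four utilization items the gap is larger. Without an ER row, and without a pre-trial window for visits, the before/after comparison announced in the text has no data behind it.

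This is a data-collection choice. An analysis plan, however detailed, cannot recover a count or a date that was not extracted.

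**Working it through.** **The plan's own figure.** The only sample-size figure concerns the medication possession ratio (MPR): SD 10 points, difference 5 points, two-sided 5%, 80% power.

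- Normal approximation: n = 2 × (1.96 + 0.84)² × 10² / 5² ≈ 63 per arm. The t-test version gives 63.8, so 64, with power 0.80.
- Dropout: 64 / 0.8 = 80 per arm, 160 in total.

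These figures reproduce and are not in dispute. The protocol gives no admission rate and no power for utilization, so what follows is illustration on assumed rates.

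**Assumptions.** Mean admissions per patient per six months m = 0.1 to 0.5. Counts are Poisson, or negative binomial with variance m + m²/k, where k = 1 is moderate and k = 0.5 strong clustering of admissions in few patients.

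**Step 1: information kept by yes/no.** With p0 the probability of no admission, p0 = (1 + m/k)^(−k), or e^(−m) for Poisson. With k taken as known, the information on the log rate from yes/no, relative to the count, is

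E = m × p0 / [(1 + m/k) × (1 − p0)].

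This becomes m e^(−m) / (1 − e^(−m)) for Poisson and 1/(1 + m) for k = 1. Example at m = 0.3, Poisson: 0.3 × 0.741 / 0.259 = 0.857. Example at m = 0.5, k = 0.5: 0.5 × 0.707 / (2 × 0.293) = 0.60.

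| m | Poisson | k = 1 | k = 0.5 |
|---|---|---|---|
| 0.1 | 0.95 | 0.91 | 0.87 |
| 0.2 | 0.90 | 0.83 | 0.78 |
| 0.3 | 0.86 | 0.77 | 0.71 |
| 0.5 | 0.77 | 0.67 | 0.60 |

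**Step 2: admissions that yes/no cannot show.** The share beyond a patient's first is 1 − (1 − p0)/m. Over the same three distributions it is 5–13% at m = 0.1, 9–23% at 0.2, 14–30% at 0.3 and 21–41% at 0.5.

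**Step 3: power at 80 per arm, rate ratio 0.5.** Yes/no is tested as two proportions. Counts are tested by a Wald test with variance (1/m1 + 1/m2 + 2/k)/80, where m1 is the control mean and m2 = 0.5 × m1.

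| control mean | yes/no | count |
|---|---|---|
| 0.1 | 0.17–0.20 | 0.18–0.20 |
| 0.2 | 0.26–0.35 | 0.30–0.36 |
| 0.3 | 0.31–0.48 | 0.38–0.50 |
| 0.5 | 0.37–0.66 | 0.50–0.72 |

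The gain from counting runs from about 0 to 13 points (0.37 to 0.50 at mean 0.5, k = 0.5). Neither coding reaches 80%.

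**Step 4: what yes/no still delivers.** The 95% half-width for a between-arm difference in the proportion with any admission is 1.96 × √(2p(1 − p)/80). That is 9 points at p = 10%, 12 at 20% and 14 at 30%. The estimate is coarse, but it exists.

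**Step 5: text against table, item by item.**

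| Utilization item in the text | Table 3 type | Pre-trial window | Trial window |
|---|---|---|---|
| Hospitalization | yes/no | yes | yes |
| ER visits | no row | – | – |
| Office visits | appointments scheduled, numeric | no | yes |
| Calls | numeric (anticoagulation unit) | yes | yes |

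A before/after change is therefore available in full for calls to that unit, in reduced form for hospitalization, and not at all for ER or office visits.

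**The case against.** The strongest reply is that any admission within six months is a legitimate endpoint, that the trial is sized on MPR and not on admissions, and that counting would not make this comparison conclusive. All of that stands. It limits the weight of the point, but it does not answer the loss of repeat admissions or the missing ER and office-visit data.

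A reader might infer more than the documents support:

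- *That change in hospitalization cannot be measured.* It can: two yes/no windows give the change in the proportion with any admission, within and between arms.
- *That events must be split into on and off treatment.* The protocol plans no such split. Keeping patients in after discontinuation suits a comparison as randomized, which needs none.
- *That inpatient days must come out of an adherence denominator.* The protocol defines no such denominator, and such a rule could properly sit in the analysis plan.
- *That no event dates exist anywhere.* The appendix on safety data makes most hospitalizations and all deaths serious adverse events, and its minimum case information includes onset date where available. The Management of Safety Data section, however, excludes subjects not exposed to the supporter's product and starts at consent. It therefore helps for rivaroxaban users in the trial window, but not for other patients or for the pre-trial window.

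Two further replies deserve an answer. Staff could apply the withdrawal cut while reading the chart; the stored yes/no would then neither show that this was done nor carry the length of observation. Counts and dates could also be extracted later if the record holds them. That is likely, since an event must be placed in time to be assigned to a window, but the protocol does not say so. It is also a reason to extract them once, at the planned reading.

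For stroke, embolus and death, repeats within six months should be rare or impossible, so the date is the main loss there.

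**Conclusion.** The point holds as a limitation of data collection. It does not undermine the trial. Table 3 restricts hospitalization to any admission per window, drops repeat admissions, and leaves events without the dates needed to apply the withdrawal rule or account for time at risk from the recorded data. At assumed means of 0.1 to 0.5 admissions per six months, yes/no keeps 67–95% of the information on the rate ratio for Poisson counts and negative binomial counts with k = 1, falling to about 60% under the strongest clustering considered. The loss is small if admissions are rare and moderate otherwise. These sizes rest wholly on assumed rates and dispersion.

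The finding on ER and office visits needs no assumption: the text promises a before/after comparison for which Table 3 lists no data. The MPR sample size is unaffected.

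**What to change.** In Table 3:

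1. Change hospitalizations from yes/no to a count with admission dates, in both windows.
2. Add the event date to stroke, arterial embolus, hemorrhage and death.
3. Add numeric rows for ER visits and office visits, in both windows.

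Compare admissions between arms as a rate, with observed time as the exposure and the pre-window count as covariate. Keep any admission as a derived summary; it can always be obtained from dated records, while the reverse is impossible.

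The cost is slightly more chart extraction, with no added patient contact for items taken from the record. Event dates are additional protected health information, and the Risk Analysis section limits collection to what the aims require. The amendment should therefore state the reason: applying the withdrawal rule, and measuring utilization over known time at risk.
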